9.3 Major Secondary Analyses

Secondary analyses will be done for two study populations. Participants randomized in Part I or assigned to the abatacept arm in Part II will comprise the enrolled population [N approximately equal to 126 (37 Part I, 89 Part II)]. The overall study population [N approximately equal to 554] will include the enrolled population and 428 patients from the CARRA Registry whose disease extension results provided the control mean in Part II.

Secondary analyses for the enrolled population

Secondary analyses will generally be conducted as planned in Part I, although estimation of treatment effects or treatment by factor differences will be imprecise, since more than 80% of participants in the enrolled population are expected to receive abatacept.

Description of the time to disease extension will include cumulative incidence curves for the composite primary outcome and for the components disease extension, uveitis, and initiation of DMARDs or other biologic medication.

Descriptive analyses will summarize participant and caregiver reported outcomes (continuous outcomes of pain interference, fatigue, upper extremity function, mobility, anxiety, depression and global health PROMIS® modules, medication side effects (JAMAR), and the CHAQ). These outcomes will be measured at baseline and follow-up visits as shown in Table 5, and will be analyzed using a mixed model for repeated measures. Preliminary analyses will be performed to identify a parsimonious covariance structure among the repeated measures. The model will include as fixed effects treatment, time, treatment x time interaction, the baseline value of the outcome and the two stratification variables, the risk categories for polyarthritis and uveitis. Time will be treated as a categorical variable. The restricted maximum likelihood (REML) method of estimation and the Kenward-Roger degrees of freedom correction will be used. Contrasts will be constructed among the model parameters to test specific hypotheses. Overall treatment effect will be assessed by testing the null hypothesis of no treatment difference averaged over time. If the treatment x time interaction is significant at $\alpha=0.10$, additional descriptive tests may be done for treatment differences at specific time-points. Since more than 80% of participants in the enrolled population are expected to receive abatacept, there will be limited statistical power to determine treatment effects on these outcomes.

Secondary analyses for the overall study population

Inclusion of data from 428 CARRA Registry patients may provide important information on the impact of treatment on time to disease extension and PROs. Since treatment assignment for the overall study population is not random, it is anticipated that causal inference techniques such as inverse probability or overlap weighting will be useful in determining the comparability of the Registry patients and participants enrolled in LIMIT-JIA.

The timing of evaluations for disease extension and PROs and missing data patterns are expected to differ between participants enrolled in LIMIT-JIA and CARRA Registry patients. Techniques such as multiple imputation may be used to enable modeling of the overall study population.

Details of the analysis of treatment effect for the overall study population will be provided in a separate SAP.

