8.2 Secondary Outcomes

8.2.1 Patient reported outcomes

Patient-reported outcomes (PROs), related to pain, fatigue, functional ability, anxiety, depression, global health, family impact, and other medication side effects will be collected and analyzed. PROMIS® measures will be used for each of the outcomes of interest where available. Caregiver/proxy-report will be obtained for participants able to complete the forms in English or in Spanish, and by self-report for children ≥ 8 years of age. The existing iPAD-based, CARRA Registry electronic PRO system will be utilized.

The following PRO instruments will be used.

- PROMIS® pediatric measures selected by the patient/family partners (pain interference, fatigue, functional ability) that have undergone preliminary validation in JIA.^{64,65}
- PROMIS® pediatric measures of anxiety, depression, and global health.
- Side effects of medications, assessed by the yes/no question 11 in the JAMAR.⁶⁶

Table 5: Description of PROs

Outcome	Measure	Timing	Source
Pain	PROMIS® pediatric pain interference	Every study visit	Parent-proxy or child (if \geq 8 years)
Fatigue	PROMIS® pediatric fatigue; short form	Every study visit	Parent-proxy or child (if \geq 8 years)
Functional Ability	PROMIS® upper extremity function and mobility	Every study visit	Parent-proxy or child (if \geq 8 years)
	CHAQ	Baseline, 6M, 12M	Parent-proxy or child (if \geq 8 years)
Anxiety	PROMIS® pediatric emotional distress – anxiety; short form	Baseline, 6M, 12M	Parent-proxy or child (if \geq 8 years)
Depression	PROMIS® pediatric emotional distress – depression; short form	Baseline, 6M, 12M	Parent-proxy or child (if \geq 8 years)
Global Health	PROMIS® pediatric global health measure (PGH-7)	Every study visit	Parent-proxy or child (if \geq 8 years)
Other medication side effects	JAMAR (Juvenile Arthritis Multidimensional Arthritis Report) question #11	Baseline, 3M, 6M	Parent-proxy or child (if \geq 8 years)

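### Section 9.3 sends a yes/no side-effect item (JAMAR question 11) to a linear mixed model meant for continuous outcomes

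*Combined protocol and SAP*

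**What the plan says.** Section 9.3, for the enrolled population, introduces the patient-reported outcomes this way: "Descriptive analyses will summarize participant and caregiver reported outcomes (continuous outcomes of pain interference, fatigue, upper extremity function, mobility, anxiety, depression and global health". The list continues: "medication side effects (JAMAR), and the CHAQ). These outcomes will be measured at baseline and follow-up visits as shown in Table 5". One model then covers every item. Its fixed effects are set out: "The model will include as fixed effects treatment, time, treatment x time interaction, the baseline value of the outcome and the two stratification variables". So are the estimation method, "The restricted maximum likelihood (REML) method of estimation and the Kenward-Roger degrees of freedom correction will be used", and the hypothesis: "Overall treatment effect will be assessed by testing the null hypothesis of no treatment difference averaged over time". The covariance is left open: "Preliminary analyses will be performed to identify a parsimonious covariance structure among the repeated measures".

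Section 8.2.1 describes the JAMAR outcome differently: "Side effects of medications, assessed by the yes/no question 11 in the JAMAR". Table 5 in that section names only that item, "JAMAR (Juvenile Arthritis Multidimensional Arthritis Report) question #11", collected at baseline, month 3 and month 6.

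The synopsis includes the JAMAR item among the secondary endpoints. Objective 2.2.1 points to a comparison with the Registry, but section 9.3 leaves the Registry-inclusive analysis to a separate SAP. The enrolled-population model is therefore the only analysis of this item specified here.

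**The concern.** A yes/no answer has variance p(1-p), which moves with its mean. A linear mixed model with one residual variance for both arms ignores this. Where the arms are of similar size the effect is often small. Here they are about 1 to 6, so the pooled variance comes almost entirely from the abatacept arm and is then applied to a usual-care arm of about 18.

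If the true rates differ, the standard error of the arm difference is wrong, in a direction that depends on which arm has more side effects. What is at stake is the estimate and interval for a named secondary endpoint on tolerability. If the text stays as it is, the analyst must either report a Gaussian mean of a 0/1 item or depart from the written plan after seeing open-label data.

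**Working it through.** **The texts side by side.** Section 8.2.1 and Table 5 make the outcome binary. Section 9.3 groups it with continuous outcomes and gives it a linear model. One could read the word continuous as covering only the PROMIS modules, but the following sentence still assigns the whole list, JAMAR included, to the same model. No link function, score or count is defined for it. The plan does use logistic regression for its binary primary outcome (section 9.2), so this looks like an oversight.

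**Arm sizes.** Sections 9.1 and 9.3 give 37 participants randomised 1:1 in Part I and 89 in Part II, all on abatacept: 37 + 89 = 126. A near-even split of 37 gives about 18 on usual care and 19 + 89 = 108 on abatacept. That is 108/126 = 86%, in line with the plan's statement that more than 80% receive abatacept.

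**Why the interval goes wrong.** For one visit and a common variance (an assumption, since section 9.3 does not mention arm-specific variances):

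- True variance of the difference: p0(1-p0)/18 + p1(1-p1)/108, with p0 for usual care and p1 for abatacept.
- Variance the model expects: [17·p0(1-p0) + 107·p1(1-p1)]/124 × (1/18 + 1/108).

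At 25%/5% (usual care/abatacept) the true variance is 0.1875/18 + 0.0475/108 = 0.01086, so the SE is 0.104. The model variance is (3.1875 + 5.0825)/124 × 0.06481 = 0.00432, so the SE is 0.066, or 63% of what it should be.

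At 5%/25% the true variance is 0.0475/18 + 0.1875/108 = 0.00438 (SE 0.066). The model variance is (0.8075 + 20.0625)/124 × 0.06481 = 0.01091 (SE 0.104), or 158% of what it should be.

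**Exact coverage of the 95% interval.** The single-visit column enumerates all outcomes (pooled-variance t, 124 df). The adjusted column averages months 3 and 6, adjusts for the baseline answer and two strata, and rests on 8,000 simulations with complete data, latent correlation 0.6, baseline rate 10% and strata without effect.

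| Usual care / abatacept (assumed) | Single visit | Adjusted, M3 and M6 |
|---|---|---|
| 25% / 5% | 75.4% | 76.9% |
| 15% / 5% | 84.8% | 81.8% |
| 20% / 10% | 88.4% | 88.3% |
| 15% / 10% | 90.3% | 91.8% |
| 10% / 10% | 96.1% | 95.4% |
| 20% / 20% | 95.5% | 95.4% |
| 10% / 15% | 97.6% | 97.4% |
| 5% / 25% | 99.6% | 99.5% |

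At equal rates of 5% to 30% the single-visit two-sided test has size 3.9% to 5.1%, so the planned null test holds.

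**Arm-specific variances do not repair it.** Single-visit Welch coverage is 94.1% at 25%/5%, but 91.0% at 5%/25%, 84.7% at 10%/10% and 68.4% at 5%/5%.

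**Score-type intervals do.** Over 20 rate pairs, Newcombe and Miettinen-Nurminen intervals each cover 95.2% to 96.8%.

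**Logistic GEE.** With the same covariates, an exchangeable working correlation and Mancl-DeRouen standard errors, coverage is 95.9% to 96.6% over six rate pairs (1,500 simulations each), counting only datasets with events in both arms. An arm had no events over both visits in 0% to 4% of datasets when the usual-care rate was 10% or more, and in 19% at 5%/25%. At a single visit the chance of no events among 18 is 0.90^18 = 0.15 at a 10% rate and 0.95^18 = 0.40 at 5%.

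**The case against.** The strongest reply is that nothing the plan promises is shown to fail. It plans a null test, and that test keeps its size. Section 9.3 does not commit to an interval, so the coverage figures concern an output that may never be produced. This stands. It limits the harm but does not make the specification right, because in a descriptive analysis the estimate and its interval are the usual product.

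Second, under-coverage needs more side effects on usual care. Both arms receive usual care (section 4.2), and section 6.2 names infection and injection-site reactions as the common effects of abatacept. Equal rates or a higher abatacept rate are therefore more to be expected, and there coverage is adequate or conservative. This also stands, although the documents give no rates and do not exclude the reverse.

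Third, some figures are fragile. At 10%/5%, coverage is 87.5% with 18 against 108, 79.9% with 19 against 107 and 91.0% with 17 against 109. The actual split is not in the documents, and the 37 is a count at October 2021, before Part I enrolment closed. The shortfalls at 25%/5%, 15%/5% and 20%/10% are steadier.

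Fourth, a per-visit risk difference drops the baseline answer and the risk strata, although most abatacept participants are non-randomised. That is a real cost, and it is why an adjusted option belongs in the fix. Section 9.3 also refers back to the Part I plan, which is not in the document, but it then states this model explicitly.

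**Conclusion.** The point holds. The plan contradicts itself on the scale of a named secondary endpoint and gives a yes/no item a model for continuous data. The mismatch is certain from the text. The size of the harm is conditional: it rests on assumed side-effect rates, a common residual variance, a split near 18 to 108, and an interval being reported.

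Under those assumptions, nominal 95% coverage runs from about 75% when usual care has a much higher rate to above 99% when abatacept does. The null test is sound. The analysis is secondary, labelled descriptive and acknowledged by the plan to have limited power. The primary analysis and sample size are untouched. It should be corrected, but it does not threaten the trial's main conclusion.

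**What to change.** Remove JAMAR question 11 from the mixed-model list in section 9.3. State that it will be summarised as the number and proportion answering yes, by arm, at baseline, month 3 and month 6. Compare arms at months 3 and 6 with a Newcombe or Miettinen-Nurminen 95% interval for the risk difference.

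If a single contrast over both visits is kept, specify a logistic GEE with arm, visit, baseline answer and the two risk strata, using a small-sample variance correction such as Mancl-DeRouen. State in advance that the per-visit interval is used if an arm has no events.

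The cost is SAP wording only, with no new data or visits. The per-visit interval is unadjusted and uses one visit at a time. The GEE uses the covariates and both visits but gives an odds ratio, so the zero-event fallback changes the effect measure. The text should say so. Neither option by itself deals with missed visits, so the handling of missing answers should be stated alongside.

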9.4 Other Planned Analyses

Other planned analyses for the enrolled population

In addition to assessment of treatment differences in PROs, other secondary outcomes include proportion of children achieving clinically inactive disease and/or remission; number of new joints with arthritis; cumulative number of glucocorticoid joint injections; serious adverse events; juvenile arthritis disease activity (JADAS) scores; elapsed time from enrollment to disease extension, uveitis or initiation of DMARD or other biologic treatment.

Sensitivity analyses will be performed to assess the impact of COVID-19 – including measures taken in response to the pandemic such as telehealth visits, missed visits or oral prednisone use on the primary study endpoint. COVID-19 infections will be included in the safety analyses.

Other planned analyses for the overall population

To be described in a separate SAP.

9.4.1 Subgroup Analyses

Subgroup analyses for enrolled population

For the primary composite outcome, a formal test of homogeneity of treatment effect among baseline risk categories is planned. Exploratory comparisons will be carried out in the ITT population for the primary outcome, the components of the primary outcome, and for the two primary PROMIS® measures (pain interference and mobility), comparing the results between subgroups in order to determine clinical and biological factors associated with each. Subgroups will include the different ILAR categories of JIA (enthesitis-related arthritis, psoriatic arthritis, and undifferentiated arthritis compared to oligoarthritis); demographic factors (age, sex, race); inflammatory markers at time of enrollment (normal or elevated ESR, CRP); presence or absence of autoantibodies (antinuclear antibody, rheumatoid factor, CCP); genetic marker human leukocyte antigen B27 (HLA-B27); the number of joints and specific joints affected prior to enrollment; and the duration of disease prior to enrollment. Statistical comparison of treatment effects in subgroups will be done by the addition of a term denoting subgroup membership in the model used to compare the two treatment arms. We will test the subgroup-by-treatment interaction at the 0.15 level. Graphical displays such as forest plots, showing treatment effects and 95% confidence limits within subgroups may be used to display results. The subgroup analyses in this study are exploratory and should be considered hypothesis-generating.

Subgroup analyses for the overall study population

To be described in a separate SAP.

9.4.2 Power, Sample Size and Type I error

The trial sample size was determined by the intended statistical comparison of the primary outcome (proportion of participants with disease extension) between the abatacept plus usual care and historical care usual care treatment arms [See Appendix: Modification of Study Design and Rationale for Discontinuing Randomization to Control Arm]. It is assumed that the proportion of participants with disease extension will be 34.3% in the usual care arm, and that

this rate will be reduced to 15% in the abatacept plus usual care arm. With 1-sided type 1 error = 0.025, 80 evaluable participants enrolled into the abatacept + usual care arm (compared with the historical control mean from 428 patients) would provide > 95% power using logistic regression. Assuming 10% of participants will not be evaluable, we will enroll up to 89 patients to receive abatacept + usual care arm. See Table 7. Hypothesis testing will be done with the Wald statistic testing the effect of the factor for treatment (abatacept + usual care, vs usual care) in the logistic model with factors for intercept and treatment.

Subgroup or other non-primary analyses may be done by inclusion of additional factors to the logistic regression model.

Table 7: Simulated power for sample sizes in the experimental arm of 10, 20, ..., 80; assuming type I error = 0.025 one-sided.

Sample size (evaluable) in experimental arm N =	Number to enroll assuming a 10% inevaluable rate	Power *
20	23	0.332
30	34	0.591
40	45	0.742
50	56	0.824
60	67	0.900
70	78	0.934
80	89	0.956

* For R_{ex} and R_c = disease extension rates in the experimental and control arms, resp. $H_0: R_{ex} = R_c = 0.343$ (estimated from the historical control group), and $H_1: R_{ex} < 0.15$ (i.e. $< R_c - 0.193$). Power was calculated by simulation of the logistic model, where extension rates followed a binomial distribution [$R_c = 0.343$, $N = 428$] in the control arm, and [$R_{ex} = 0.15$, N (for $N = 20, 30, \dots, 80$ as shown in the table)]. Type I error is 0.025, one-sided.

A sample size of eighty evaluable patients (all enrolled in the abatacept + usual care arm) will provide > 95% power to reject the null hypothesis that the disease extension rate is $\geq 34.3\%$ assuming one-sided type I error ≤ 0.025 and a true disease extension rate in the abatacept + usual care arm $\leq 15\%$. To allow for an inevaluable rate up to 10%, enrollment will be expected to be approximately eighty-nine patients.

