
9.5.4 Interim Analysis

Interim analyses, with stopping boundaries for futility and efficacy, are planned after approximately 40% ($n = 32$) and 80% ($n = 64$) of Part II participants have been followed for one year. Details will be provided prior to initiation of Part II.

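### If the Wald statistic, the only test the plan names, is carried to the first interim look (about n = 32), one event counts for less than two and zero events count for nothing

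*Combined protocol and SAP*

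**What the plan says.** Section 9.2 compares abatacept with registry controls in a logistic model whose only factor is treatment, and reports the odds ratio with 95% limits. Section 9.4.2 fixes the test: "Hypothesis testing will be done with the Wald statistic testing the effect of the factor for treatment". It offers no alternative for sparse or empty cells. The design figures in the same section are a control arm where the "proportion of participants with disease extension will be 34.3% in the usual care arm" and the expectation that "this rate will be reduced to 15% in the abatacept plus usual care arm", tested at one-sided 0.025 with 80 evaluable participants. On Table 7, its footnote says "Power was calculated by simulation of the logistic model".

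Section 9.5.4 says "Interim analyses, with stopping boundaries for futility and efficacy, are planned after approximately 40" per cent (n = 32) and 80 per cent (n = 64) of Part II participants have one year of follow-up. It leaves the details until before Part II starts. It gives no boundary family, spending function, futility rule or interim test statistic.

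**The concern.** An efficacy look should treat fewer treated events as stronger evidence. The logistic Wald statistic does not do so when events are few, because the standard error of the log odds ratio grows faster than the log odds ratio itself. With no events the estimate diverges and Z collapses towards zero.

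The first look has only 32 treated participants, and a much better result than planned would put the event count in exactly this range. If the deferred interim rules adopt the one statistic the plan names, the look would be least sensitive when the treatment effect is largest.

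**Working it through.** **Inputs.** From Section 9.4.2: control rate 34.3% in 428 patients, taken as 147 events because 0.343 × 428 = 146.8; abatacept rate 15%; one-sided 0.025; final n = 80. From Section 9.5.4: looks at 32 and 64. The efficacy boundary is not stated, so a range is assumed in step 4.

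**1. Reproduce Table 7.** I enumerated the two binomials exactly, rejecting when Wald Z < −1.96 and scoring zero-event samples as Z = 0. For n = 20, 30, …, 80 this gives 0.327, 0.587, 0.738, 0.835, 0.898, 0.935 and 0.958. Table 7 has 0.332, 0.591, 0.742, 0.824, 0.900, 0.934 and 0.956, so the plan's figures reproduce. At n = 20, counting zero-event samples as rejections would give 0.365, because P(0 of 20 at 15%) = 0.85^20 = 0.039. The stated 0.332 fits non-rejection better. That suggests, without proving, that the simulation treated a perfect result as a failure.

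**2. Wald at n = 32 with x events.**

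Z = [ln(x/(32−x)) − ln(147/281)] / √(1/x + 1/(32−x) + 1/147 + 1/281)

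- x = 2: (−2.708 + 0.648) / √0.5437 = −2.060 / 0.737 = −2.79
- x = 1: (−3.434 + 0.648) / √1.0426 = −2.786 / 1.021 = −2.73
- x = 0: the fitted model gives a coefficient of −22.9, a standard error of about 14,000 and Z = −0.002 (one-sided p about 0.50)

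From two events to one, the effect grows by 2.786/2.060 = 1.35 and the standard error by 1.021/0.737 = 1.39.

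**3. Other statistics on the same tables.** The score statistic is Z = (x/32 − 147/428) / √[p(1−p)(1/32 + 1/428)], with p = (x + 147)/460. At x = 0 this is −0.3435/0.0855 = −4.02.

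| Events in 32 | Wald, abs. Z | Score, abs. Z | Likelihood ratio, abs. Z | Fisher, one-sided p |
|---|---|---|---|---|
| 0 | about 0 | 4.02 | 5.08 | 0.0000026 |
| 1 | 2.73 | 3.65 | 4.28 | 0.000042 |
| 2 | 2.79 | 3.28 | 3.71 | 0.00033 |
| 3 | 2.64 | 2.91 | 3.21 | 0.0017 |
| 4 | 2.39 | 2.54 | 2.74 | 0.0065 |

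Treating 34.3% as a known constant moves the Wald maximum only to 2.82.

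**4. Assumed first-look bounds (one-sided 0.025, 40% information).**

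- Not reachable by Wald at n = 32: Lan–DeMets O'Brien–Fleming 3.36; classical O'Brien–Fleming 3.20; Haybittle–Peto 3.0 or 3.29; power family with rho = 3, 2.95; Hwang–Shih–DeCani with gamma = −4, 2.90.
- Reachable: power family with rho = 2, 2.65, by 1–2 events; Pocock, 2.27, by 1–4 events. Zero events cross neither.
- Timing matters. The Wald maximum is 2.97 at n = 36 and 3.13 at n = 40.

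**5. Probability of stopping for efficacy at n = 32.**

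| Bound and statistic | Stops at | True rate 15% | True rate 10% | True rate 5% |
|---|---|---|---|---|
| 3.36, Wald | never | 0 | 0 | 0 |
| 3.36, score | 1 event or fewer | 3.7% | 15.6% | 52% |
| 3.0, Wald | never | 0 | 0 | 0 |
| 3.0, score | 2 events or fewer | 12.2% | 36.7% | 78.6% |

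Zero of 32 has probability 0.0055, 0.034 and 0.19 at true rates of 15%, 10% and 5%.

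**6. Later analyses.** At n = 64 the Wald maximum is 3.94, and 1–12 events (but not 0) pass an assumed second-look bound of 2.26. At n = 80 as a single analysis, exact power is 0.958 (Wald) and 0.961 (score), and exact type I error is 0.0222 and 0.0237.

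**The case against.** The strongest reply is that the interim rules do not exist yet. Section 9.5.4 defers them, and the Wald sentence sits in the sample-size section, next to the justification of n = 80. It does not expressly govern the interims. That stands, and it makes the point conditional. But Wald is the only statistic named, so a drafter of the interim rules would naturally take it over.

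Three stronger readings are tempting, and the documents do not support them.

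- **That the early-stopping rule does not work, or can never stop the trial.** This needs Wald at the interim, a first-look bound above about 2.8 and a look close to n = 32. The plan states no bound and gives the timing only as approximate. A milder bound or a look at 36 to 40 changes the answer.
- **That 0/32 would fall on the futility side.** No futility rule is given, whether on the Z scale, by conditional power or otherwise. A fit with a standard error near 14,000 is visibly degenerate, and the monitoring board's procedures are in a separate document.
- **That the trial's power suffers.** With assumed bounds of 3.36/2.26/2.03, no futility stopping and the control fixed at 147/428, enumerating all three looks at a true 15% gives overall power of 0.975 for both statistics. Type I error is 0.016 for both, and expected sample size is 66.5 (Wald) against 65.3 (score). With 3.0/3.0/1.97, expected sample size is 72.0 against 67.9. What is at stake is mainly a delay to the second look.

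It is also fair that the score test is not the only answer. The likelihood-ratio statistic is also monotone here.

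**Conclusion.** The point holds in conditional form. If the named Wald statistic is used at the first look, its ordering of results is wrong below two events, and 0/32 registers as no evidence under any boundary. If the first-look bound also exceeds about 2.8 and the look falls at about n = 32, no result can stop the trial for efficacy there.

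The size depends on the true rate. At the planned 15% under a bound of 3.36, the loss is 3.7 percentage points of first-look stopping probability; it is 15.6 points at 10% and 52 points at 5%. At n = 64 only zero events are affected, and the final analysis is not materially affected. The calculations assume 147 control events and the bounds listed above, none of which the plan states. The change is worth making because it is nearly free and the interim rules are still to be written.

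**What to change.** In Section 9.5.4, with a cross-reference in 9.4.2, name the score statistic (or the likelihood-ratio statistic) for treatment from the same logistic model as the test at both interim looks. Preferably use it at the final analysis too, so that one statistic runs throughout. The choice should be made together with the boundary: at n = 32 and a bound of 3.36, likelihood ratio stops at two events or fewer and score at one or fewer.

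Keep the odds ratio as the estimate, but specify profile-likelihood or exact confidence limits when an arm has no events, since the Wald limits fail there as well. Confirm overall type I error across the three looks with the chosen statistic and boundary. The single-analysis figures at n = 80 do not settle that.

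The cost is a few sentences and one enumeration or simulation, with the same model and no additional participants. Table 7 was simulated for Wald, so it needs a footnote or a rerun if the final test also changes; exact power at n = 80 would move only from 0.958 to 0.961 with the score test.
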